Representative tumor biopsies are required from patients with locally advanced BCC at screening, at week 8, and again either at the time of investigator-assessed clinical or clinical/RECIST response (if before 24 weeks), or at 24 weeks if the patients are still in the study without evidence of progression. At any time during a patient's participation in the study, an optional tumor biopsy may be requested to clarify the response status of the patient. In addition, biopsy of any accessible target lesion(s) is highly recommended at the time of progression and will be used for exploratory molecular and histologic analyses. The sites, number, and technique of representative biopsies will be determined by the investigator on the basis of the size and location of the accessible lesions. It is recommended that any areas suspicious for residual disease be biopsied, as well as areas which appear to be free of disease. These biopsies will be reviewed by site's pathologist. For additional details regarding the guidelines for tissue biopsy, see Appendix G.

g. Laboratory Assessments

Local Laboratory Assessments. Samples for hematology, serum chemistry, urinalysis, and pregnancy will be analyzed at the study site's local laboratory.

- Hematology (hemoglobin, hematocrit, platelet count, red blood cell [RBC] count, white blood cell [WBC] count, and percent or absolute differential count [neutrophils, eosinophils, lymphocytes, monocytes, basophils, and other cells])
- Serum chemistry (including glucose, blood urea nitrogen [BUN], creatinine, sodium, potassium, magnesium, bicarbonate, calcium, total protein, albumin, total bilirubin, alkaline phosphatase, AST, and ALT)
- Urinalysis (pH, specific gravity, glucose, protein, ketones, and blood)
- Pregnancy test:

All women of childbearing potential (including those who have had a tubal ligation) will have a serum pregnancy test at screening, followed by urine pregnancy tests on Day 1, and every 4 weeks. A positive urine pregnancy test must be confirmed with a serum pregnancy test.

Central Laboratory Assessments. Samples tissue of locally advanced BCC patients in the expansion phase obtained at baseline and 8-week visits will be sent to a central laboratory for analysis.

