- b. A complete physical exam includes evaluation of the head, eyes, ears, nose and throat; cardiovascular, dermatological, musculoskeletal, respiratory, gastrointestinal, and neurological systems.
- c. Vital signs include pulse, systolic and diastolic blood pressure while the patient is in a seated position, respiratory rate, and temperature.
- d. Tumor assessments must be performed at screening and every 8 weeks thereafter. Assessments should include an evaluation of all sites of disease. Patients in the metastatic BCC cohort will undergo tumor assessments per the Response Evaluation Criteria in Solid Tumors (see Appendix B). Patients in the locally advanced BCC cohort will undergo tumor assessments per the composite tumor response criteria (see Appendix C).
- e. Instructions for obtaining digital photographs are given in Appendix H.
- f. For patients with locally advanced BCC, a baseline tumor biopsy must be performed in accordance with guidelines (see Appendix G). Perform biopsy again on Week 8. Repeat biopsy either at best clinical response if achieved prior to Week 24 or at Week 24. A tumor biopsy is recommended at the time of progression.
- g. Hematology consists of hemoglobin, hematocrit, platelet count, red blood cell (RBC) count, white blood cell (WBC) count, and percent or absolute differential count (neutrophils, eosinophils, lymphocytes, monocytes, basophils, and other cells).
- h. Serum chemistry includes glucose, blood urea nitrogen (BUN), creatinine, sodium, potassium, magnesium, bicarbonate, calcium, total protein, albumin, total bilirubin, alkaline phosphatase, AST, and ALT.
- i. Urinalysis includes pH, specific gravity, glucose, protein, ketones, and blood.
- j. Measurement of serum 25-hydroxyvitamin D (25[OH]D or calcidiol) is required at screening. Follow-up 25(OH)D measurements will be performed every three months. Patients found to have serum 25-hydroxyvitamin D (25[OH]D) concentration lower than 20 ng/mL during the screening period should receive vitamin D supplement.
- k. For women of childbearing potential, including those who have had a tubal ligation. A serum pregnancy test is required at screening and urine pregnancy tests will be performed at specified subsequent visits. If a urine pregnancy test is positive, it must be confirmed by a serum pregnancy test.

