APPENDIX G

GUIDELINES FOR TISSUE BIOPSY IN PATIENTS WITH LOCALLY ADVANCED BASAL CELL CARCINOMA

Representative tumor biopsies are required for patients in the locally advanced basal cell carcinoma (BCC) cohort at the following timepoints:

- At screening, Week 8 and
- Either at the investigator's assessment of best clinical response or best clinical/RECIST response, if occurring prior to 24 weeks,

or

| Required Tumor Biopsy | Screening (Day -14 to -1) | Week 8 (± 3 Days) | Clinical Response if before Wk 24 | Week 24 (±3 Days) | At disease progression |
|---|------------------------------|-----------------------|---|-------------------------|---------------------------|
| Tumor biopsy for Hh pathway measurement (for laBCC patients in expansion cohort only) | Х | Х | | | |
| Tumor biopsy for tumor response assessment | Х | | Х | Х | X^1 |

At 24 weeks, if patient is still in study and is without evidence of progression

¹Recommended for all locally advanced BCC patients.

At any time during a patient's participation in the study, an optional tumor biopsy may be requested to clarify the response status of a patient. In addition, biopsy of any accessible target lesion(s) is highly recommended at the time of progression.

The sites, number, and technique of representative biopsies will be determined by the investigator on the basis of the size and location of the accessible lesions. It is recommended that any areas suspicious for residual disease be biopsied, as well as areas which appear to be free of disease. These biopsies will be reviewed by site's pathologist.

Two separate biopsies should be obtained rather than splitting the biopsies for response assessment and Hh pathway activity measurement.

For Hh pathway activity measurement, at least one and up to two punch biopsies of at least 4 mm in size, or 14-gauge or larger core needle biopsies should be obtained. It is recommended that approximately 0.1 cm³ of the tissue specimen, which should yield sufficient mRNA for this study. Tumor samples should immediately be snap frozen in

either liquid nitrogen or dry ice following surgical resection and stored at -80° C or below in a proper pre-cooled cryovial. It is highly recommended that biopsies should be snap frozen immediately and to be maintained frozen. Samples should be transported to Oncocyte Corporation per the "Sample Storage and Shipping Instructions" attached to this Guideline.

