7. ANALYSIS POPULATIONS

The following analysis sets/populations will be used in this trial:

- **Safety population:** All enrolled patients who receive any amount of study drug. Unless otherwise noted, all safety analyses will be performed using Safety population.
- **Dose determining population:** All patients treated in the Phase 1 treatment-durationincrement part of the study. The dose determining population will be used to determine the primary outcome of the study, the RP2D dose.
- Efficacy population: All patients who are treated in the treatment-duration-increment cohort or the expansion cohort and whose pathologist's interpretation of baseline biopsy is consistent with BCC. Patients without interpretable baseline tissue, as determined by the pathologist, or by pathology report from the study site documenting a pathologist's determination of BCC will be excluded from the Efficacy population. Such patients' efficacy data will be presented in by-subject listings but excluded from all summary analyses. Objective response will be assessed separately for patients with mBCC vs. locally advanced BCC.
- **Relative Dose Intensity (RDI) population:** All patients treated in the expansion cohort including those who complete the protocol-defined treatment or discontinue treatment due to adverse events or for disease progression. Patients who are discontinued for any reason other than for adverse events or for disease progression will not be included in the relative dose intensity assessment. The RDI population will be used for the assessment of relative dose intensity defined for each cycle.

For some objectives (pharmacodynamics, biomarker parameters) a subgroup of patients of the efficacy population with respective baseline and post-baseline measurements will be used as described in section 11.9.1 below.

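### The protocol requires a Week 8 tumour biopsy from run-in patients with locally advanced BCC, but its own biopsy table assigns that sample no endpoint

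*Protocol*

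**What the plan says.** The requirement to take the biopsy is stated by disease type, not by study part:

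- Protocol 12.1f: "Representative tumor biopsies are required from patients with locally advanced BCC at screening, at week 8".
- Appendix A, footnote f: "For patients with locally advanced BCC, a baseline tumor biopsy must be performed in accordance with guidelines", and then "Perform biopsy again on Week 8".
- Appendix G, opening text: "Representative tumor biopsies are required for patients in the locally advanced basal cell carcinoma (BCC) cohort at the following timepoints". Screening and Week 8 head the list that follows.

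The use of the Week 8 sample is stated more narrowly:

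- The Appendix G table has two rows. The row "Tumor biopsy for Hh pathway measurement (for laBCC patients in expansion cohort only" is marked at screening and Week 8. The row "Tumor biopsy for tumor response assessment" is marked at screening, at clinical response before Week 24, at Week 24 and at progression, but not at Week 8.
- Protocol 12.1g, central laboratory: "Samples tissue of locally advanced BCC patients in the expansion phase obtained at baseline and 8-week visits will be sent to a central laboratory".

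The bullet directly after that sentence describes histology review and GLI1 profiling at baseline and 8 weeks for locally advanced patients, and does not mention the expansion. The Hedgehog objective in section 8 is also unrestricted.

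SAP section 7 says that for pharmacodynamic objectives "a subgroup of patients of the efficacy population with respective baseline and post-baseline measurements will be used". It points to SAP 11.9.1 for the description, but 11.9.1 leaves the GLI1 analysis to a separate report.

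**The concern.** A research biopsy should have a stated purpose for each patient who undergoes it. The protocol treats biopsy as an invasive procedure that can itself cause adverse events (16.1.1, 16.2.1), and Appendix C has to separate ulceration caused by biopsy from ulceration that counts as progression. For a run-in patient with locally advanced disease, the body text and the flowchart require the Week 8 sample, while the appendix that says what the sample is for excludes that patient.

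A site cannot satisfy both. If it omits the biopsy, it departs from 12.1f. If it takes the biopsy, it holds tissue with no assigned assay or destination, and nothing says whether to freeze or fix it.

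**Working it through.** The plan gives no numerical target for GLI1, so the check is a cross-reading followed by a count.

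**Step 1. Does each text reach a run-in patient with locally advanced BCC at Week 8?**

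| Place | What it governs | Run-in patient covered? |
|---|---|---|
| Protocol 12.1f | Taking the biopsy | Yes; no limit by study part |
| Appendix A, footnote f | Taking the biopsy | Yes; no limit by study part |
| Appendix G, timepoint list | Taking the biopsy | Unclear; cohort could mean the disease group or the expansion cohort |
| Appendix G table, Hedgehog row | Use of the tissue | No; expansion only |
| Appendix G table, response row | Use of the tissue | No Week 8 entry for anyone |
| 12.1g, central-laboratory sentence | Shipping for analysis | No; expansion only |
| 12.1g, GLI1 bullet | Profiling and histology | Yes, if read alone |

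Two texts require the sample without qualification. Both texts that limit its use by study part exclude the run-in patient. Only the GLI1 bullet points the other way, so the protocol also disagrees with itself on use.

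**Step 2. Could the sample serve a GLI1 pair anyway?** Not as planned. The only screening biopsy Appendix G marks for a run-in patient is the response biopsy: at least 3 mm by punch, fixed and paraffin embedded. The Hedgehog biopsy is a separate sample, at least 4 mm by punch and snap frozen, and Appendix G says not to split one biopsy between the two purposes. Sections 9.2 and 15.2 define the GLI1 endpoint in fresh-frozen tissue. No frozen baseline partner is planned for the run-in Week 8 sample. Section 12.1g and the title of 14.1 name paraffin-embedded tissue as an alternative, but the readable text says nothing on combining it with frozen tissue.

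**Step 3. How many patients?** Let k be the number of run-in patients with locally advanced disease.

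- Run-in size: 3 to 6 (protocol 15.6).
- Expansion: 10 + 10 = 20. Total: 3 + 20 = 23 to 6 + 20 = 26, which agrees with the approximately 26 in protocol section 18.
- Disease split of the run-in: not given, so k runs from 0 to 6.
- Planned locally advanced patients: 10 + k, that is 10 to 16. The affected share is k/(10 + k), from 0 to 6/16 = 37.5%.

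The upper end assumes that every run-in patient is locally advanced and still on study at Week 8. Replacements under section 10.4 are not counted.

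**The case against.** **Appendix G may already settle it.** Section 12.1f and footnote f refer to Appendix G for the biopsy guidelines, Appendix C says biopsies follow it, and its table is the list of required biopsies. If cohort there means the expansion cohort, run-in patients owe no Week 8 biopsy. This reading is plausible. It does not remove the problem, because 12.1f and footnote f carry no such limit and a site working from the flowchart would take the sample.

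**The tissue is not wholly unused.** Section 12.1f has the site pathologist review the biopsies, and Appendix C uses on-study biopsies to separate complete from partial response in clinical responders. The first scheduled tumour assessment is at 8 weeks, so a response could be seen then. This stands in part, and it is why the claim is limited to Appendix G assigning no endpoint. A biopsy prompted by response belongs to the clinical-response column, not to the fixed Week 8 requirement.

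**It may be too late.** SAP section 6 records early termination during the expansion, which follows the run-in. Protocol wording can no longer spare run-in patients already biopsied. That is correct, and it lowers the practical value of the protocol change. The analysis-set statement can still be made.

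**Conclusion.** The contradiction is real. Followed as written, 12.1f and footnote f put 0 to 6 run-in patients through an invasive Week 8 biopsy to which Appendix G assigns no endpoint, beyond site-pathologist review. The range rests on the stated run-in size and on the unstated disease split; if no run-in patient has locally advanced disease, nobody is affected. The RP2D determination and the response analysis are unaffected.

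A reader might infer three stronger points, which the documents do not support:

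- **That usable GLI1 pairs are being discarded.** No Hedgehog biopsy is marked at screening for run-in patients, so there is no planned fresh-frozen pair to lose.
- **That assaying run-in tissue would tighten the GLI1 estimate.** With 13 or 16 pairs instead of 10, the standard error would fall by 12% or 21% at equal SD (√(10/13) = 0.877; √(10/16) = 0.791). That requires 3 or 6 run-in patients, all locally advanced and all evaluable, plus baseline samples that are not planned.
- **That the SAP uses a different denominator from the protocol.** The Efficacy population does include the run-in, but SAP section 7 restricts the subgroup to patients with both measurements. A run-in patient whose tissue is not assayed drops out, so the rule is compatible with expansion-only sampling.

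**What to change.** Make 12.1f, 12.1g, Appendix A footnote f and Appendix G agree, so that the Week 8 biopsy is required only of patients whose tissue has a stated use. As the Appendix G table and the central-laboratory sentence now stand, that means:

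1. Add the expansion-cohort limit to the Week 8 requirement in 12.1f, in footnote f and in the Appendix G timepoint list. The screening, response and Week 24 biopsies are outside this change.
2. Put the same limit in the GLI1 bullet of 12.1g.
3. State in the SAP or in the separate GLI1 report that the analysis set is the patients with assayed baseline and Week 8 tissue. Where run-in Week 8 tissue was taken, state what was done with it.

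The cost is a few phrases in the protocol and one sentence in the SAP or GLI1 report, with no added patients, visits or assays. In a study still recruiting its run-in, it would spare up to 6 patients one biopsy. Extending Hedgehog sampling to the run-in is not proposed, because under Appendix G it would add a separate screening biopsy for each of those patients.

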APPENDIX H

DIGITAL PHOTOGRAPHIC PROCEDURES FOR SERIAL PHOTOGRAPHIC DOCUMENTATION OF BASAL CELL CARCINOMA

(Refer to the most current version of the Photo Manual)

APPENDIX I

ECOG PERFORMANCE STATUS

| GRADE | ECOG PERFORMANCE STATUS |
|-------|---|
| 0 | Fully active, able to carry on all pre-disease performance without restriction |
| 1 | Restricted in physically strenuous activity but ambulatory and able to carry out work of a light or sedentary nature, e.g., light house work, office work |
| 2 | Ambulatory and capable of all selfcare but unable to carry out any work activities; up and about more than 50% of waking hours |
| 3 | Capable of only limited selfcare; confined to bed or chair more than 50% of waking hours |
| 4 | Completely disabled; cannot carry on any selfcare; totally confined to bed or chair |
| 5 | Dead |

APPENDIX J

EQUATION FOR CALCULATING AN ESTIMATED GLOMERULAR FILTRATION RATE

The Cockcroft and Gault formula:

CrCl (mL/min) =

(140 - Age) x Weight x 0.85 (if female)

72 x Serum Creatinine

Abbreviations/ Units:

CrCl (creatinine clearance) = mL/minute

Age = years

Weight = kg

Serum creatinine = mg/dL

[If serum creatinine is in μ mol/L, multiply the above Cockcroft and Gault equation with 1.4 for females or 1.23 for males]

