 - Surgery: Previous surgery is permitted provided that a minimum of 28 days (4 weeks) have elapsed between any major surgery and date of registration, and that wound healing has occurred.
 - Cytotoxic Chemotherapy: There is no limit to the number of prior regimens received.
 - Other Systemic Therapy: Previous treatment with Hh pathway antagonists is not allowed (except for Smoothened inhibitors). There is no limit to the other prior therapies received (see Appendix K).

Patients must have recovered (to baseline or \leq grade 1) from all reversible toxicity related to prior chemotherapy or systemic therapy and have adequate washout as follows:

Longest of one of the following:

- Two weeks,
- 5 half-lives for investigational agents,
 - For anti-cancer therapies with half-lives > 8 days, a washout period of at least 28 days will be acceptable,
- Standard cycle length of standard therapies.
- 10. Patients with nevoid BCC syndrome (Gorlin syndrome) may enroll in this study but must meet the criteria for locally advanced or metastatic disease listed above.
- 11. For patients with locally advanced BCC, willingness to consent to biopsy of tumor(s) at baseline and during the study, as mandated by the protocol.
- 12. Adequate hematopoietic capacity, as defined by the following:
 - Hemoglobin ≥ 9.0 g/dL and not transfusion dependent
 - Platelets $\geq 100,000/\text{mm}^3$
 - Absolute neutrophil count ≥ 1500 cells/mm³
- 13. Adequate hepatic function, as defined by the following:
 - AST and ALT \leq 2.5 times upper limit of normal (ULN) or \leq 5 times ULN if liver metastases are present

- Total bilirubin $\leq 1.5 \text{ x}$ ULN or within 3x the ULN for patients with Gilbert disease
 - Albumin $\geq 3.0 \text{ g/dL}$
- 14. Adequate renal function, as defined by the following:
 - Renal: calculated creatinine clearance >45 mL/min for patients between 18 and 70 years old with abnormal, increased, creatinine levels (Cockcroft-Gault formula; Appendix J). For patients who are greater than 70 years old, investigator judgment may be used to assess the renal risk of study participation.
- 15. Women/men of childbearing potential must have agreed to use two effective contraceptive methods while on study and for 6 months after the last dose of CX-4945 (see Appendix D for definition of women of childbearing potential and acceptable and unacceptable methods of contraception)

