18. ADMINISTRATIVE STRUCTURE

Senhwa Biosciences Inc., will sponsor this study. A contract research organization (CRO) will perform study management, including project management, statistical programming, clinical monitoring, medical monitoring, data monitoring, and data management. One hundred percent source document verification will be conducted for all enrolled patients. Approximately 26 patients will be enrolled at approximately 6 sites in the United States.

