6. SAMPLE SIZE DETERMINATION

In the treatment-duration-increment part of the study, a 3+3 study design will be utilized, therefore approximately 3-6 patients will be enrolled to define the RP2D.

In the expansion part of the study, a total sample size of 20 patients is proposed; 10 patients with local advanced BCC and 10 patients with metastatic BCC. Assume that CX-4945 is of no interest if its true response is 5% or lower, the proposed sample size for each sub-population will provide an 80% confidence interval of (5.5%, 45.0%) given that there are 2 responses out of the 10 patients. This would provide adequate evidence to suggest that additional studies with this agent may be warranted.

10 patients with metastatic BCC were planned in the expansion part of the study, but only 2 were enrolled due to early termination.

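### Appendix J's note for creatinine in µmol/L does not agree with its own Cockcroft-Gault formula: the constant for women is 1.4 where the formula implies about 1.05, and the wording leaves 72 and 0.85 in place

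*Protocol*

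**What the plan says.** Protocol Appendix J prints clearance in mL/min as (140 − age) × weight, times 0.85 for women, divided by "72 x Serum Creatinine", with creatinine in mg/dL. A bracketed note covers creatinine in µmol/L: "multiply the above Cockcroft and Gault equation with 1.4 for females or 1.23 for males". It does not say that 72 or 0.85 should be dropped.

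Inclusion criterion 14 (Protocol 10.1.1) refers to this appendix and requires "calculated creatinine clearance >45 mL/min for patients between 18 and 70 years old with abnormal, increased, creatinine levels". Older patients are handled differently: "For patients who are greater than 70 years old, investigator judgment may be used to assess the renal risk of study participation".

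On the unit sites would meet in practice, Protocol 12.1 g says: "Samples for hematology, serum chemistry, urinalysis, and pregnancy will be analyzed at the study site's local laboratory". No reporting unit for creatinine is given there. Protocol section 18 states: "Approximately 26 patients will be enrolled at approximately 6 sites in the United States".

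**The concern.** Converting mg/dL to µmol/L rescales creatinine by the same factor for everyone. The ratio of the women's result to the men's, at equal age, weight and creatinine, must therefore stay at the formula's 0.85. The note's constants have the ratio 1.4/1.23 = 1.14. Used as replacement constants, they give a woman a higher clearance than a comparable man, while the formula directly above gives her a lower one.

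There is a second fault. The value 1.23 makes sense only as a constant that already contains 1/72, but the note says to multiply the equation as printed, which still has 72 in it.

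At stake is the protocol's only numeric renal entry limit. An overstatement of 14% or 34% looks plausible on a worksheet and errs towards admission, so a woman whom the mg/dL formula places at or below 45 mL/min could be recorded as meeting the limit.

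**Working it through.** **Inputs.** From Appendix J: 0.85 for women, 72, and the note's constants 1.4 (women) and 1.23 (men). From criterion 14: the limit of more than 45 mL/min. The core check needs no outside figure. The factor 88.4 µmol/L per mg/dL is not in the documents and is used only as a cross-check.

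**The male constant reproduces as a replacement for 1/72.** 1.23 × 72 = 88.56 µmol/L per mg/dL, close to the assumed 88.4 (88.4/72 = 1.228).

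**The female constant does not reproduce.** Replacing 0.85/72 requires 0.85 × 1.23 = 1.0455 (1.0436 with 88.4). If 0.85 is kept as a separate factor, the constant is 1.23 for both sexes. Neither gives 1.4.

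**Three readings of the note, each compared with the mg/dL form:**

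| Reading | Women | Men |
|---|---|---|
| (a) Constant replaces 1/72 and, for women, 0.85 | 1.4/1.0455 = 1.339, 34% too high | agrees |
| (b) Constant replaces 1/72 only; 0.85 kept | 1.4/1.23 = 1.138, 14% too high | agrees |
| (c) Literal: 72 and 0.85 both kept | 88.56/1.4 = 63.3 times too low | 88.56/1.23 = 72.0 times too low |

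**At the eligibility limit, for women.** A computed 45 mL/min corresponds by the mg/dL form to:
- reading (a): 45/1.339 = 33.6
- reading (b): 45/1.138 = 39.5

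With 88.4 in place of 88.56 these are 33.5 and 39.5.

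**Illustrative patient** (assumed inputs: woman, 65 years, 60 kg, creatinine 110 µmol/L, taken to count as raised at her laboratory). (140 − 65) × 60 = 4500.

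| Calculation | Clearance (mL/min) | Above 45? |
|---|---|---|
| mg/dL form: 4500 × 1.0455/110 | 42.8 (42.7 with 88.4) | no |
| (a): 4500 × 1.4/110 | 57.3 | yes |
| (b): 4500 × 0.85 × 1.4/110 | 48.7 | yes |
| (c): 4500 × 0.85 × 1.4/(72 × 110) | 0.7 | no |

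The creatinine at which she reaches 45 mL/min is 4500 × 1.0455/45 = 104.6 µmol/L by the mg/dL form. It is 4500 × 1.4/45 = 140 under (a) and 4500 × 0.85 × 1.4/45 = 119 under (b).

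**If the source page reads 1.04.** Reading (a) would then agree with the formula, since 1.04 is 0.85 × 1.23 to within rounding. The literal reading would still fail: 88.56/1.04 gives results about 85 times too low for women, and 72 times too low for men as before.

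**The case against.** The strongest reply is that 1.4 may be a one-character slip for 1.04, in the source or in text extraction; other characters in the extracted protocol are visibly altered. If so, the 34% and 14% errors disappear. What remains is loose wording whose literal result, below 1 mL/min in the example, would probably be noticed and errs towards exclusion. This stands as a reason to look at the source page first. It does not rescue the instruction to multiply the equation as printed, which is wrong for both sexes whichever digit is right.

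Reading (b) can also be called strained, because constants given separately by sex suggest that sex is already included. That is fair, but reading (a), the more natural one, gives the larger error.

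The remaining objections concern reach, and they have force:
- All planned sites are in the United States, and the protocol's other laboratory limits use conventional units (g/dL for hemoglobin and albumin, ng/mL for vitamin D), so the note may never have been used.
- Patients over 70, patients with normal creatinine, and results in mg/dL are unaffected. Men are affected only under the literal reading.
- The example depends on 110 µmol/L counting as raised locally, and the documents give no upper limit of normal.
- Exclusion criterion 5 and serum chemistry every 4 weeks give further protection.
- The SAP, section 6, says of the metastatic expansion cohort that "only 2 were enrolled due to early termination", so little may be left to change prospectively.

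These points lower the practical priority. None makes the note agree with the formula.

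**Conclusion.** The concern holds. No reading of the note as printed reproduces the appendix's own mg/dL result for women, and the literal reading fails for both sexes. On the two non-literal readings clearance in women is overstated by 34% or 14%, enough to reverse an eligibility decision near 45 mL/min.

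The inconsistency follows from the document's own constants. The size depends on which reading a site adopted and on 1.4 being what the source page shows. The number of patients affected cannot be determined from the documents and may be zero, because the laboratories' reporting unit is not stated.

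The sample size and the primary endpoint are untouched, and no SAP analysis uses creatinine clearance. The note should be corrected because an entry criterion cites the appendix, but it does not threaten the trial's conclusions.

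**What to change.** First check the source page for a transcription slip. Then replace the bracketed note with an instruction such as: *If serum creatinine is in µmol/L, convert it to mg/dL (divide by 88.4) and use the equation above.* The 88.4 is an assumed standard factor; the appendix's own constants imply 88.56. An equivalent form is (140 − age) × weight × 1.23 (men) or 1.04 (women), divided by creatinine in µmol/L, with neither 72 nor 0.85. The limit in criterion 14 stays as it is.

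If enrolment is closed, ask the sites which creatinine unit they used at screening, recompute clearance for any patient assessed with the µmol/L note, and report any eligibility decision that would have differed.

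The cost is one line in an appendix if the protocol is amended again, or otherwise one query to approximately 6 sites. No analysis changes.
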